Researcher Study Protocol

Official Title: The Effect of Mobile Software "Let's Move" Program Developed Based on Transtheoretical Model on Sedentary Life Behaviors of University Students

NCT ID: not yet assigned

Record Verification: 14.07.2022

SUMMARY and KEYWORDS:

Sedentary life means a physically inactive, sedentary life and is the fourth leading risk factor for global deaths. It is reported that 70% to 85% of young people between the ages of 15-24, who make up 15.6% of the population of our country, are sedentary. This rate does not meet the physical activity guidelines recommended by the World Health Organization for young people. Sedentary lifestyle causes physical, biological and mental problems, increases the prevalence of non-communicable diseases and negatively affects academic achievement. Integration of technology into human life in the health dimension; It aims to reduce the obstacles of individuals to change their unhealthy behaviors and to increase their motivation to gain healthy behaviors. The Transtheoretic Model (TTM) is an easy-to-use and proven effective model for changing the prevalence of activity. Schools are the most effective medium to reach young individuals. However, considering the density of the school population and the inadequacy of school health nurses in our country; New approach techniques and innovative strategies are needed to reduce costs and save time. Therefore, in the first stage of this twostage research, it was aimed to develop the TTM-based 'Hadi Move' mobile software program and to test the effect of the mobile software program developed in the second stage on changing the sedentary life behaviors of university students. The universe of this research consisted of 290 students studying at a foundation university in Istanbul. The sample was calculated using the G-power (3.1.9.4) program. By taking 10% more of the sample, 97 students in the experimental group and 97 students in the control group will be randomly assigned through the SPSS program. TTM-based "Let's Move" mobile software program developed for the experimental group will be applied for 12 weeks. The effectiveness of the program will be evaluated with pre-test, post-test and follow-up test, International Physical Activity Questionnaire, daily step count smart bracelet and sedentary lifestyle TTM Sedentary Life Scales (Stages of Change, Change Process Scale, Self-Efficacy and Decisional Balance Scale). At the end of the research, the effectiveness of the 'Hadi Move' mobile software program developed in this research in changing the sedentary life will be tested. In addition, it is aimed to increase the number of steps, decrease in sedentary behaviors and make an active lifestyle permanent. All initiatives developed for TTM sedentary life behavior change stages will be made into a book and the results of the experimental research will be published, contributing and providing evidence to the international literature.

OBJECTIVE/REASON:

The aim of the project is to develop the "Let's Move" mobile software program based on the Transtheoretic Model (TTM) and to test the effect of the developed program on changing the sedentary life behaviors of its students.

Project Goals

- The developed TTM based 'Let's Move' mobile software program will be effective in changing the sedentary behaviors of students.
- The number of steps of the experimental group will increase.
- The physical activity Metabolic Equivalent (MET) scores of the experimental group will increase.
- The ratio of inactive and minimally active students in the experimental group will decrease, and the ratio of students in the very active category will increase.
- The percentage of students in the experimental group TTM behavior change preparation and action phase will increase.
- The cognitive change processes scores of the experimental group will increase.
- The behavioral change processes scores of the experimental group will increase.
- The self-efficacy score of the experimental group will increase.
- Decision-making utility perception score of the experimental group will decrease.
- The decision-making harm perception score of the experimental group will increase.
- The proportion of those with normal Body Mass Index (18.5-24.99) in the experimental group will increase.
- The International Physical Activity Questionnaire (IPAQ) scores of the experimental group will increase.
- Total body muscle ratio of the experimental group will increase.
- The body fat ratio of the experimental group will decrease.

SUBJECT and SCOPE

Sedentary lifestyle is an important behavioral problem that threatens health and is reported to be common among young people (WHO, 2020; Ceylan, 2020; Kim et al., 2020; Han et al., 2017; Prochaska et al., 2017). University years include adolescence and young adulthood. In order to reach the healthy adults of the future, it is very important to spend these periods active, to gain healthy lifestyle behaviors and to make them permanent. Adopting an inactive lifestyle of young people causes many non-communicable diseases (diabetes, hypertension, hyperlipidemia, etc.) in later ages (Kleis et al. 2022; Güler, 2022). For this reason, developing

an active lifestyle and changing an inactive lifestyle during the youth years are the most important components of reaching healthy societies.

When the studies are examined, it is seen that the majority of the studies conducted to reduce sedentary life focus on adults aged >30 years (Kleis et al., 2022; Fabio et al., 2020; Tanyeri, 2019; Menekli et al., 2019; Kim et al., 2018; Ya -Ke Wu&Nain-Feng Chu, 2015; Wang et al., 2015; Savcı et al., 2006; Andersan et al., 2006) and a limited number of experimental studies based on the Transtheoretic Model (TTM) for university students (Kim&Lee, 2022; Kim et al., 2021; Chen et al., 2020; Lee et al., 2020; Ceylan, 2020; Başakçı, 2019).

The Transtheoretic Model argues that change is a process, not a result, that the individual changes behavior by going through certain stages, and that in order to be successful in change, appropriate initiatives should be planned for the stage of change that the individual is in. The model recommends appropriate biopsychosocial and behavioral interventions by evaluating the individual's readiness for change with the stages of change questionnaire and the self-efficacy and determination levels with scales. It constantly monitors the stage of change that the individual has reached as a result of the initiatives, offers initiatives to prevent returns and to make the behavior permanent (Han et al., 2017; Procha et al., 2017; Başakçı, 2019; Kim et al., 2020; Ceylan, 2020; Lee et al., 2020).

LITERATURE REVIEW:

In the examination made with the keyword Transtheoretic Model (TTM) on the YÖK Thesis website; It has been observed that 34 theses based on TTM were conducted in our country between the years 2008-2021. One of these studies was the validity and reliability study of the transtheoretic model sedentary life scales (Tok, 2017), and seven of them aimed to increase physical exercise (Ünver, 2021; Sönmez, 2020; Ceylan, 2020; Tanyeri, 2019; Serin, 2017; Baysal, 2013; Kafalı). , 2009) was found to be oriented. It was determined that three of them were aimed at preventing obesity (Ceylan, 2020; Başakçı, 2019; Cangöl, 2016;), and 12 of them aimed at quitting smoking (Deniz, 2021; Sözer, 2020; Ersoy, 2019; Yalçınkaya, 2019; Avcı, 2018; Çavuşoğlu, 2018). ; Durmaz, 2017; Çamözü, 2017; Taş, 2015; Koyun, 2013; Prosecutor Minister, 2013; Güngörmüş, 2008). Others are sun protection (Duran, 2019; Aygün, 2012), reproductive health (Karatana, 2021; Aksoy, 2019), safe cycling (Erdem, 2021), diabetes education (Tosun, 2015), controlled internet use (Bayrak, 2021).), prevention of suicidal behavior (Bahar, 2021), education for patients with hypercholesterolemia (İncazlı, 2019), safe drug administration (Arslan, 2017) and nurse navigation program in cancer screening

(Temuçin, 2017). The results of all these studies show that TTM is an effective model for changing behavior.

As a result of the literature review, TTM-based mobile software program to increase physical activity could not be reached in the national and international literature. However, there are applications for changing exercise, physical activity, smoking, weight management and nutritional behaviors with TTM-based web-based platforms (Smith et al., 2014; Chen et al., 2017; Kenned et al., 2017; Jimoh et al., 2018; Ludwig et al., 2018; He et al., 2021; Choi et al., 2021; Allman-Farinelli et al., 2016; Hebden et al., 2014; Epton et al., 2014; Partridge et al., 2015; Peyman et al., 2018).

Choi et al. (2021) developed a smartphone application (AnSim) that sends messages based on a transtheoretical model for healthy eating, physical activity, stress relief and smoking cessation for individuals with coronary artery disease. They stated that health promotion approaches using mobile technology have great potential (Choi et al., 2021). Prochaska et al (2007) developed the TTM-based LiveWell program to improve healthy lifestyle behaviors such as exercise, eating and stress management in university students. The program is a computer online intervention program that plans dynamic initiatives suitable for each student and their readiness for behavior change, with personalized questions and feedback. At New York University, the LiveWell program was applied to all students with the motto of 'healthy campuses'. At the end of the program, it was shown that there was a significant increase in students' self-efficacy and quality of life values (Prochaska et al., 2017).

In a study conducted by Başakçı (2019) to determine the effect of TTM-based initiative enriched with whatsapp messages on weight management; It has been determined that there is an increase in the physical activity levels of individuals, a decrease in the Body Mass Index values and a positive change in the nutritional behaviors in the desired direction (Başakçı, 2019). According to the results of the study; They suggested that more work should be done by developing whatsapp messages suitable for TTM change stages and adding mobile health applications. Ceylan (2020) conducted a TTM-based quasi-experimental research by sharing trainings, messages, videos and images to increase physical activity in adolescents via WhatsApp. According to the research findings, it was found that the adolescents progressed in the exercise change stages, increased their self-efficacy and benefit perception scores, and decreased their harm perception scores. He also stated that individuals continue physical activity despite the pandemic conditions (Ceylan, 2020). Lee et al. (2017) developed a smart

phone program containing special nutritional information messages based on a transtheoretical model to prevent and manage obesity in primary school students.

ORIGINAL VALUE

The difference of the 'Let's Move' mobile software program, which is planned to be developed in this research, is that it provides ease of use and includes special initiatives for the behavior change stage of the individual (not thinking, thinking, preparation, acting, continuing). The mobile software program includes five stage-specific educational videos that increase the individual's motivation for change and self-efficacy, appropriate physical activity visuals, stimulating or motivating messages, and daily step counts. In addition, students will complete the International Physical Activity Questionnaire once a week through the program, and the program will calculate students' weekly activity status (inactive, minimally active and very active). Students will be able to send messages to the researcher through the program.

The most basic literature gains of the research; It provides an accessible, effective and technologically innovative program prepared by health professionals to reduce sedentary life. The program is evidence-based; It will include practices that are entertaining, interesting, encouraging, empowering individuals to live actively and enabling/supporting them to take responsibility. It is thought that if the program, which is created with a multidisciplinary perspective, can be delivered to young individuals free of charge, it will be effective in increasing physical activity. In addition, all initiatives developed for TTM sedentary life behavior change stages will be made into a book and the results of the experimental research will be published, contributing and providing evidence to the international literature.

This experimental research consists of two stages. In the first stage of the research, it was aimed to develop TTM-based 'Let's Move' mobile software program and to test the effect of the mobile software program developed in the second stage on changing the sedentary life behaviors of university students.

WIDE IMPACT/ADDED VALUE

Effect Type	Effect	Projected Time to Achieve the Effect
-------------	--------	--

 Social/Cultural Impact: Contribution to Quality of Life, Contribution to Sustainable Environment and Energy, Contribution to the Improvement of Welfare or Education Level, Solutions to an Important Social Problem at Country or World Level, etc. 	 If the developed mobile application program is found effective, the program link will be shared free of charge via the apple store. It will contribute to the development of active living habits of young people. The program, created with a multidisciplinary perspective, will contribute to young individuals getting accurate information about physical activity and adopting this information. It is thought that it will contribute to the prevention of obesity, which is an important problem in the world and in our country. 	• 0-18 months
 Academic Impact: New R&D Decisions, National/International R&D Collaborations, Change in Number and Qualification of Researchers, Contribution to University- Industry Cooperation etc. 	 The program content tested in the research can be adapted to different age groups by working with software engineers. Research can be done by other researchers using it on different university students. If the program is found effective, it can be adapted to different languages and opened to international use. The program can be developed and expanded on the basis of the Android operating system by working with software engineers. 	• 6-12 months
 Economic Impact: Potential Sectoral Application Areas, Global Market Forecasts, Employment Contribution, Competitiveness (Effect on Export, Import Substitution, Formation of New Firms, Triggering Foreign Capital Investment, etc.) 	 It will be cost effective by saving time and personnel to reduce sedentary life behaviors in young people. Health expenses will decrease due to the prevention of physical and mental diseases caused by sententary life. Since it is a mobile software that students use constantly, its use will be easier, faster and can be expanded. 	• 12-18 ay months
Long Term Effects	 If the program is effective in reducing sedentary lifestyles, it will be cost-effective by reducing chronic diseases (diabetes, hypertension, etc.) that increase health costs in adulthood. 	• 5-10 years

MATERIALS AND METHODS:

- 1. Type of research; The research will be conducted with methodological and experimental research design.
- The place and time of the research; The research was planned to be carried out between September 2021 and September 2023 with university students studying in Istanbul Beykent University Vocational School health program.
- 3. The universe of the research; The universe of the research consists of Anesthesia Program (n=57), Operating Room Services Program (n=64), Oral and Dental Health Program (n=89), Medical Imaging Techniques (n=27) and First and Emergency Aid Program at Istanbul

Beykent University Vocational School. (n=53) university freshman students studying in departments with a high number of students and meeting the criteria for inclusion in the research constituted N=290. Students who meet the inclusion criteria and volunteer to participate will be included.

4. Sample; The sample of the study was calculated with the G-power (3.1.9.4) program, means: difference between two independent means analysis. When the effect size was 0.5, type error $\alpha = 0.05$, power 1- $\beta = 0.95$, the sample size was found to be 176 (experimental group 88, control group 88). Considering the sample loss that may occur due to various reasons, it was decided to include 194 (experimental group 97, control group 97) more than 10% of the sample. The groups will be randomly assigned to the experimental control groups through the SPSS program.

5. Inclusion, Exclusion, and Exclusion Criteria

5.1.Inclusion criteria for the study;

- First year students studying in Istanbul Beykent University Vocational School health program between September 2021 and September 2023,
- ➤ 18-25 years old,
- Being in the inactive (category 1) and minimally active (category 2) categories according to the International Physical Activity Evaluation Questionnaire,
- Not included in any physical activity program,
- Do not have any physical (orthopedic, chronic diseases, etc.) and mental problems diagnosed by a doctor,
- Accepting the measurement of body weight, height, body fat and muscle ratio and calculation of BMI before starting the research, at the 12th week and at the 6th month after its completion,
- > Agreeing to use pedometer (pedometer),
- > Having an iPhone, iPod touch and android based smart phone,
- ➢ Have an active internet connection on their phone,
- Students who voluntarily agree to participate in the research will be formed.

5.2. Exclusion and Exclusion Criteria;

➢ Willingness to leave the research.

6. Data Collection Tools and Format

Data Collection Tools; Data of the study, Socio-demographic characteristics questionnaire (Appendix 1), Transtheoretic Model (TTM) Sedentary Life Stages of Change (Appendix-2), TTM Sedentary Life Change Process Scale (Appendix 3), TTM Sedentary Life Self-Efficacy Scale (Appendix- 4), TTM Sedentar Life Decisional Balance Scale (Annex-5) and International Physical Activity Questionnaire (IPAQ) (Annex-6). The height of the students will be measured with a telescopic height meter and a scale that measures body weight, fat and muscle ratios. Step counts will be collected with the Smart Bracelet.

Data Collection Path; Students in the universe will be contacted through class representatives and informed about the right to research, and they will be invited to apply the data collection forms. Ethics committee permission, institutional permission document, voluntary consent form, socio-demographic questionnaire form, TTM Sedentary Life Scales and International Physical Activity Questionnaire will be sent to the accepted participants in the form of online forms via Google Drive.

6.1.Socio-demographic Questionnaire Form (Annex 1)

The sociodemographic characteristics diagnosis form was created by examining the relevant literature (Han et al, 2017; Tok, 2017; Baysal, 2013; Tanyeri, 2019; Ceylan, 2020). The form consists of 32 questions. In the questionnaire, there are research-oriented questions that question socio-demographic characteristics and participation in physical activity.

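### No outcome or time point is primary and the 0.5 effect size belongs to none; two goals run against the scale scoring, and goals 2–14 leave out the control arm

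*Protocol*

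**What the plan says.** **Goals.** Objective/Reason lists 14 Project Goals. The first is that the program will be effective. Goals 2–14 each state a direction for the experimental group, with no comparator and no time point. Examples are "The ratio of inactive and minimally active students in the experimental group will decrease" (goal 4), "The cognitive change processes scores of the experimental group will increase" (goal 6) and "Decision-making utility perception score of the experimental group will decrease" (goal 9). Goal 10 expects the harm score to rise.

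**Time points.** The Summary says "The effectiveness of the program will be evaluated with pre-test, post-test and follow-up test" and ranks neither later test. Section 5.1 gives "before starting the research, at the 12th week and at the 6th month after its completion", but only for body weight, height, fat, muscle and BMI.

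**Sample size.** Section 4 uses a "difference between two independent means analysis" with alpha 0.05 and power 0.95. It begins "When the effect size was 0.5" and gives no outcome, unit, standard deviation, time point, source or sidedness. The result is 88 per arm, raised to 97.

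**Outcomes and analysis.** Section 9 lists the dependent variables without ranking them. Section 10 compares the arms by t test or Mann-Whitney U and sets one significance level, p<0.05.

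**Entry.** Section 5.1 requires "Being in the inactive (category 1) and minimally active (category 2) categories according to the International Physical Activity Evaluation Questionnaire". Section 6.2.5 starts the very active level at 3001 MET.

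**Decisional balance.** Section 6.2.4 and the scale appendix read a high utility score as making behaviour change more likely, and a high harm score as making it less likely.

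**The concern.** A sample size computed from one standardised difference implies one continuous outcome, compared between arms at one time. The protocol does not say which. With 13 goals, at least two later assessments and one unadjusted threshold, a single favourable p-value on any of them could be offered as support for goal 1, and nothing written beforehand would say whether it was the result the trial was sized to find.

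Two further faults in the same list affect how a result would be read. If the scoring text is right, a student moving toward change would tend to show utility rising and harm falling, so success would be recorded as failure on goals 9 and 10. And goals phrased for one arm can be ticked off by movement that the control arm shares.

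**Working it through.** **1. Reproducing the plan's sample size.** Inputs from section 4: d = 0.5, alpha = 0.05, power = 0.95, two independent means, 1:1. With n = 88 per arm the noncentrality is d√(n/2) = 0.5 × √44 = 3.317, on 2 × 88 − 2 = 174 degrees of freedom.

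| Test | Critical t | Power at 88 per arm (noncentral t) | n per arm for 0.95 |
|---|---|---|---|
| One-sided 0.05 | 1.654 | 0.951 | 88 |
| Two-sided 0.05 | 1.974 | 0.910 | 105 |

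So 176 is reproduced only as a one-sided test. The allowance is 176 × 1.10 = 193.6, rounded to 194. The calculation is a between-arm contrast of one continuous variable. It does not describe the three proportion goals (activity category, stage of change, BMI category).

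**2. Goals against the dependent-variable list.** Goals 2–14 make 13 goals. Section 9 also contains 13 variables: steps, MET category, stage, self-efficacy, benefit, harm, four MET scores (walking, moderate, severe, total), BMI category, fat and muscle. They are not the same 13. Section 9 splits the MET score into four and leaves out the cognitive and behavioural change-process scores of goals 6 and 7, although the Summary and section 6 name that scale.

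**3. Chance of at least one significant goal when nothing works.** Between-arm tests, two-sided 0.05, 13 goals, one time point. If independent, 1 − 0.95^13 = 0.487. Counting only results in the favourable direction, 1 − 0.975^13 = 0.280. The protocol gives no correlations, so a common correlation ρ is assumed. Conditioning on a shared normal factor u, the two-sided chance is 1 − E{[Φ((1.96 − √ρ·u)/√(1−ρ)) − Φ((−1.96 − √ρ·u)/√(1−ρ))]^13}. The favourable-only chance drops the second Φ.

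| Assumed ρ | Any significant | Favourable only |
|---|---|---|
| 0 | 49% | 28% |
| 0.3 | 42% | 21% |
| 0.5 | 33% | 17% |
| 0.7 | 24% | 12% |

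If goals 3 and 12 are one measure, 12 goals remain and the independent figure is 1 − 0.95^12 = 46%. For comparison, one test has a 2.5% chance of a favourable false positive.

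**4. Directions of goals 9 and 10.**

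| | Goal expects | Scoring text: a high score means |
|---|---|---|
| Utility | fall | behaviour change more likely |
| Harm | rise | behaviour change less likely |

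The modules in section 7 speak of the harm of sedentary life (to be raised or kept high) and, from the preparation phase on, of its benefit (to be lowered). That agrees with the goals. The scale sections define utility and harm as those of changing behaviour. The two usages point in opposite directions.

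**5. The activity-category goal.** If the IPAQ used for entry is also the pre-test, the very active share is 0% at baseline and cannot fall. Some students selected below a cut will lie above it on re-measurement with no program effect, so the goal as worded could be met by regression to the mean. Under the planned arm comparison this does no harm: with selection at entry, no program effect and 88 per arm, simulated false-positive rates were 4–5% for t, Mann-Whitney and chi-square tests.

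**The case against.** **The goals are expectations, not decision rules.** The protocol does not call them success criteria, and randomisation, sizing and testing are all between arms. This stands. A reader might infer from the wording that a within-group analysis is planned. Sections 4 and 10 do not support that, so the missing comparator is loose wording.

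**The very active share need not start at 0%.** This also stands. Section 7 has the experimental group complete the IPAQ again inside the program (screen 3), and the protocol does not say which administration is the pre-test. If it is the in-program one and the administrations are equally correlated, entry selection produces no rise between pre-test and post-test. The point is therefore conditional.

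**Multiplicity belongs in a statistical analysis plan, and 49% assumes independence.** Partly right. Several goals share the IPAQ or the body scale, so the correlated figures are the more realistic, and how p-values are adjusted may be settled elsewhere. But a protocol that states a sample size should say which outcome it was computed for.

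**The schedule may have been lost.** Section 8 is visibly broken off in the text at hand, and arm-by-arm timing may have stood there. The goals, sample-size and analysis sections are intact.

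**The modules support goals 9 and 10.** They do, which is why the directions cannot simply be called wrong. They still conflict with the protocol's own scoring text.

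**Conclusion.** The point holds in this form. No outcome or time point is primary, the 0.5 effect size is attached to none, and one p<0.05 covers an unranked list that omits two of the goals' own measures. With no true effect, at least one of the 13 goals would reach significance at one time point with probability 49% under independence and about 24–42% at assumed common correlations of 0.7–0.3. Favourable results alone give 12–28% (correlation 0.7 to 0). The correlations and two-sided testing are assumptions. The direction conflict in goals 9 and 10 is plain on the text and needs no assumption.

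The experimental-arm wording is a lesser fault. Nor does any of this show that 176 is miscalculated: it is right for a one-sided test, but the sidedness is unstated. It should be fixed, with moderate confidence given the damaged section 8.

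**What to change.** - Name one primary outcome and time point, measured in both arms and compared between them, for example daily steps read from the bracelet at the 12-week post-test. Say that the reading comes from the device, since screen 7 also lets participants enter counts themselves.
- In section 4, tie d = 0.5 to that outcome and state the sidedness. If tests are two-sided, restate power at 88 per arm as about 91%; keeping 95% would need 105 per arm.
- Label all other outcomes secondary.
- Reword goals 2–14 as differences between the experimental and control groups at a stated time, and say which IPAQ administration is the pre-test.
- Reconcile goals 9 and 10 with section 6.2.4 and the appendix, stating whether utility and harm refer to changing behaviour or to sedentary life.
- Add the change-process scores to section 9.

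This is wording in the goals and in sections 4, 6.2.4 and 9, provided both arms are measured at the chosen time. The cost is that secondary goals carry less confirmatory weight, and that the stated power is slightly lower if testing is two-sided.
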